#### **5.2.1.1.** Pharmacokinetics

Plasma concentrations of BPN (geometric mean) for the first 36 hours post-dose after single SC administration of CAM2038 q1w are presented in Table 1, respectively (Study HS-11-426 and HS-13-487). Although, the BPN release following CAM2038 q1w SC depot injections have a relatively smooth gradual onset relative to SL BPN formulations, BPN peak plasma concentrations ( $C_{max}$ ) across doses were observed within the first 24 hours post-dose for both the q1w formulation.

Table 1 Plasma concentrations of buprenorphine (geometric mean) after single subcutaneous administration of CAM2038 q1w to healthy subjects under naltrexone blockade

Time after dose	Plasma concentrations of buprenorphine (ng/mL)					
(h)	CAM2038 q1w 8 mg	CAM2038 q1w 16 mg	CAM2038 q1w 32 mg			
Pre-dose	< 0.025	< 0.025	< 0.025			
0.5	0.0759	0.253	0.220			
1	0.119	0.396	0.391			
2	0.257	0.722	0.748			
4	0.568	1.39	1.83			
6	0.767	1.63	2.61			
10	1.40	2.84	4.42			
24	1.65	2.84	5.00			
36	1.11	2.02	3.76			

Source: Study HS-11-426 h = hour; q1w = once weekly

Table 2 and Table 3 summarize observed and predicted BPN after single dose (Table 2) and repeat administration (Table 3) of CAM2038 q1w SC injection and SL BPN (administered as Subutex®) in healthy volunteers under naltrexone blockade. Although there are inherent differences in the pharmacokinetic profiles for daily-, weekly-, and monthly-administered products, pharmacokinetic results from Study HS-11-426 (Study Report HS-11-426) and Study HS-13487 (Interim Study Report HS-13-487) presented below, suggest that the pharmacokinetic profiles of the q1w formulation are similar with respect to steady state Cmax and Ctrough of BPN after SL administration. Based on these similarities, the current study will examine the opioid-blocking effects of only the CAM2038 q1w formulation.

Version: 2.0, 17NOV2015 Page 26 of 99

Table 2 Observed and predicted buprenorphine exposure after single administration of SC CAM2038 q1w, SC CAM2038 q4w, and SL Subutex® in healthy subjects

		Geometric Mean (geometric CV%)			
Treatment	Study	C max (ng/mL)	Ct (ng/mL) a	AUC inf (ng*h/mL)	
SC CAM2038 q1w					
8 mg	HS-11-426	1.7 (36)	0.30 (26)	166 (20)	
16 mg	HS-11-426	3.1 (49)	0.61 (25)	335 (13)	
16 mg	HS-13-487	3.1 (46)	0.58 (25)	NC	
24 mg		4.2 b	$0.86^{\rm b}$	487 b	
32 mg	HS-11-426	5.3 (45)	1.1 (24)	638 (12)	
SC CAM2038 q4w					
64 mg	HS-13-487	3.8 (60)	0.45 (57)	1360 (33)	
96 mg		5.2 b	0.69 b	1960 b	
128 mg	HS-13-487	6.6 (68)	0.93 (33)	2550 (26)	
160 mg		7.9 b	1.2 b	3120 b	
SL Subutex					
8 mg	HS-11-426	4.3 (32)	0.25 (38)	NC	
16 mg	HS-11-426	6.7 (62)	0.38 (36)	NC	
24 mg	HS-11-426	7.1 (19)	0.49 (39)	NC	
8 mg	HS-13-487	4.4 (41)	0.26 (35)	NC	
16 mg	HS-13-487	5.9 (31)	0.37 (44)	NC	
24 mg	HS-13-487	8.2 (60)	0.54 (44)	NC	

 $\overline{AUC_{inf}}$  = are under the plasma concentration-time curve from time 0 to infinity;  $C_{max}$  = maximum plasma concentration;  $C_t$  = plasma concentration at time t;  $C_t$  = coefficient of variation;  $C_t$  = Not calculated;  $C_t$  = sublingual

Table 3 Observed and predicted buprenorphine exposure after steady state administration of SC CAM2038 q1w, SC CAM2038 q4w, and SL Subutex® in healthy subjects

		Geometric Mean (geometric CV%)				
Treatment	Study	C ss,max (ng/mL)	C ss,av (ng/mL)	C ss,t (ng/mL)		
SC CAM2038 q1v	v					
8 mg		1.7ª	$1.0^{b}$	0.45 a		
16 mg	HS-13-487	4.3 (44)	2.1 (24)	0.84 (22)		
24 mg		5.2ª	2.9 b,c	1.4 a		
32 mg		6.9 a	3.8 b	1.8 a		
SC CAM2038 q4v	v	 				
64 mg		3.9 a	2.0 b	1.1 a		
96 mg		5.8 a	$2.9^{\mathrm{b,c}}$	1.6 a		
128 mg		7.8 a	3.8 b	2.1 a		
160 mg		9.8 a	4.6 b,c	2.7 a		
SL Subutex		 				
8 mg	HS-11-426	4.7 (29)	1.1 (34)	0.61 (46)		
16 mg	HS-11-426	6.3 (49)	1.6 (37)	0.79 (58)		
24 mg	HS-11-426	7.8 (37)	2.3 (29)	1.2 (44)		
8 mg	HS-13-487	4.7 (36)	1.2 (33)	0.68 (52)		
16 mg	HS-13-487	6.7 (47)	1.9 (33)	1.1 (46)		
24 mg	HS-13-487	8.5 (54)	2.7 (34)	1.6 (40)		

 $C_{ss,max}$  = maximum plasma concentration at steady state;  $C_{ss,av}$  = average plasma concentration during a dosing interval at steady state;  $C_{ss,t}$  = plasma trough concentration at steady state;  $C_{ss,t}$  = plasma trough concentration at steady state;  $C_{ss,t}$  = coefficient of variation;  $C_{ss,t}$  = pharmacokinetic

a. Ct at 7 days for SC CAM2038 q1w, Ct at 1 day (24 hours) for SL Subutex®

b. Predicted from linear regression analysis of logarithmic pharmacokinetic variable vs. logarithmic dose

a. Predicted by simulation from a nonlinear mixed effects pharmacokinetic model describing observed pharmacokinetic data.

[figure not shown]
b. Predicted and calculated from AUCinf after single dosing and assuming time-independent pharmacokinetic.

c. Predicted from linear regression analysis of logarithmic pharmacokinetic variable vs. logarithmic dose.

Figure 1 below provides graphical illustrations of observed and predicted plasma BPN concentrations for different doses of CAM2038 q1w, CAM2038 q4w, and SL BPN (Subutex®) over 28 days.

Figure 1 Observed steady state arithmetic mean  $C_{max}$  and  $C_{trough}$  of buprenorphine after sublingual administration of Subutex®, and observed and predicted steady state plasma concentration profiles after subcutaneous administration of CAM2038 q1w and CAM2038 q4w based on data from Studies HS-11-426 and HS-13-487 (semi-logarithmic scales)

Figure 1A

Version: 2.0, 17NOV2015 Page 28 of 99

Figure 1B

[figure not shown]
[figure not shown]

Figure 1C

Version: 2.0, 17NOV2015 Page 29 of 99

 $C_{max}$ = maximum plasma concentration;  $C_{trough}$ = trough plasma concentrations; q1w= once weekly dosing Geometric mean observed steady state  $C_{max}$  and  $C_{trough}$  for Subutex® from HS-11-426 and HS-13-487 Predicted plasma concentration versus time profiles for CAM2038 q1w from single and repeat dose data in HS-13-487 Observed steady state plasma concentration versus time profiles for CAM2038 q1w 16 mg from HS-13-487 Predicted steady state plasma concentration versus time profiles for CAM2038 q4w from single-dose data in HS-13-487

# 5.3. Study Rationale

Opioid drug dependence is a major health and social issue and is often a chronic medical condition that requires long-term maintenance treatment. An important aim of the treatment programs for opioid drug dependence is to reduce illicit drug use, reduce the associated harms and stabilize patients pharmacologically to allow them to engage in psychosocial interventions to assist in their recovery. Successful treatment can decrease morbidity and mortality, improve patients' quality of life, and reduce the burden on society. Moreover, individuals with opioid use disorder often engage in higher risk behaviors such as injecting with used syringes and needles, and thus expose themselves to high risk of transmission of infectious diseases, including human immunodeficiency virus (HIV) and hepatitis C.

Clinical studies have reported that BPN is effective at attenuating the effects of subsequently administered opioids, including those of acute doses of morphine up to 120 mg for up to 29.5 hours (Jasinski et al., 1978). Buprenorphine has also demonstrated the ability to dose-dependently decrease the effects of hydromorphone (Walsh et al., 1995; Bickel et al., 1988). These studies indicate that BPN (at doses ranging from 2 to 32 mg SL BPN) can attenuate the effects of hydromorphone, including subjective effects and euphoria in a dose-dependent manner. Furthermore, it was suggested that some therapeutic benefit of opioid attenuation was evident after the first dose.

The present study will investigate the presence, duration, and degree of full mu-opioid agonistic effect blockade provided by CAM2038 q1w administered at therapeutic doses for opioid maintenance therapy in patients with opioid use disorder.

Version: 2.0, 17NOV2015 Page 30 of 99

### 6. STUDY OBJECTIVES

# 6.1. Primary Objective

The primary objective of the study is:

To evaluate the degree of opioid blocking effects of CAM2038 q1w following administration of intramuscular (IM) hydromorphone (6 mg and 18 mg) compared to administration of 0 mg hydromorphone (placebo) on subjective opioid effects in subjects with opioid use disorder, as measured by the primary measure, Drug Liking visual analog scale (VAS).

# 6.2. Secondary Objectives

The secondary objectives of this study are:

- To evaluate the degree of opioid blocking effects of CAM2038 q1w following administration of IM hydromorphone (6 mg and 18 mg) compared to administration of placebo on subjective opioid effects in subjects with opioid use disorder, as determined by the secondary outcome measures.
- To explore the relationship between plasma BPN concentration and blockade of the subjective opioid effects of hydromorphone.
- To examine the safety and tolerability of CAM2038 q1w when co-administered with hydromorphone.

Version: 2.0, 17NOV2015 Page 31 of 99

### 7. INVESTIGATIONAL PLAN

# 7.1. Overall Study Design and Plan

This is a multi-site, randomized, double-blind, repeat-dose Phase 2 study to evaluate the degree and duration of action of multiple doses of CAM2038 q1w in blocking the effects of a mu opioid agonist (hydromorphone) in patients with moderate or severe opioid use disorder. The study will involve 4 phases: Screening, Qualification, Treatment, and Follow-up.

Within 4 weeks of initiating screening, subjects will be admitted to a clinical research unit (CRU) for the Qualification Phase. Following check in to the CRU, subjects will be transitioned to a short-acting oral opioid, IR morphine 30 mg, (administered 4 times daily [QID]), for a minimum of 3 days and a maximum of 7 days (Qualification Phase described in detail in Section 7.1.2). One additional dose of IR morphine 30 mg may be administered for the first 3 days of stabilization, as needed, at the investigator's discretion. After stabilization on IR morphine 30 mg, all subjects will complete a 3-day Qualification/Baseline Hydromorphone Challenge Session which will involve IM administration of 3 doses of hydromorphone (Treatment A: 0 mg [placebo], Treatment B: 6 mg and Treatment C: 18 mg) administered once daily (Day -3, Day -2, and Day -1) in a randomized, double blind, crossover manner, with each hydromorphone administration separated by approximately 24 hours (described in detail in Section 7.1.4).

Following the Qualification/Baseline Hydromorphone Challenge Session, eligible subjects will receive CAM2038 q1w at doses of 24 mg or 32 mg (randomized in a 1:1 ratio to 1 of 2 groups). Subjects will receive once weekly SC injections of CAM2038 q1w for 2 weeks (injections on Day 0 and Day 7) and will remain inpatient in the CRU for up to 25 days (including Qualification Phase), during which time 4 Hydromorphone Challenge Sessions (3 consecutive days each) will be conducted on Days 1 to 3, Days 4 to 6, Days 8 to 10, and Days 11 to 13, respectively. Safety and pharmacodynamic assessments will be performed on each day of the Hydromorphone Challenge Sessions at multiple timepoints beginning at pre-dose until approximately 5 hours post-dose. Plasma samples to quantify BPN and norbuprenorphine levels will also be obtained approximately 60 minutes prior to hydromorphone dosing on each day of the Hydromorphone Challenge Sessions.

Subjects will be discharged on Day 14 and a follow-up phone interview will be conducted on approximately Day 21.

The degree of hydromorphone dose tolerability will be determined based on the site-specific study Investigator's review of the subject's oximetry data, vital signs, behavior, and physical demeanor.

To ensure adequate enrollment and address potential inconvenience to subjects, all subjects will receive appropriate compensation for time and travel expenses related to attendance at study visits. All costs of study participation, including study medications will be covered.

Version: 2.0, 17NOV2015 Page 32 of 99

## 7.1.1. Screening Visits (Day -31 to Day -11):

Medical and eligibility screening will occur within roughly 3 weeks of check in to the inpatient Qualification Phase (Day -10, Day -9, Day -8, Day -7, or Day -6). At the first Screening Visit, subjects will provide written informed consent to participate in the study before any protocol-specified procedures or assessments are completed. Screening will include standard medical screening procedures, complete medical/psychosocial history, urine drug screen (UDS) and detailed substance use and treatment, using timeline follow-back methods (Fals-Stewart et al., 2000), as outlined in Table 4. Screening may occur over several outpatient visits. Subjects may be rescreened at the Investigator's discretion.

### 7.1.2. Qualification Phase

## 7.1.2.1. Day -10 to Day -1

During the Qualification Phase, subjects will be admitted to a CRU for a stabilization period starting on Day -10 during which all subjects will be stabilized on a short-acting oral opioid (i.e., morphine) to suppress opioid withdrawal. Subjects will receive IR morphine 30 mg, QID for a total daily dose of 120 mg; subjects will be permitted to receive an additional dose of IR morphine 30 mg dose (total daily dose of 150 mg), as needed (PRN) for the first 3 days only. At inpatient check-in, ancillary medications will be made available for symptomatic relief of withdrawal (see Table 5Error! Reference source not found.Error! Reference source not found. for the list of allowed medications). Subjects will receive IR morphine 30 mg (as outlined above) for a minimum of 3 days and a maximum of 7 days prior to entering the Qualification/Baseline Hydromorphone Challenge Session, dependent on the individual's underlying level of dependence.

During this stabilization period, subjects will be monitored carefully for safety. Before each scheduled IR morphine 30 mg dose is administered, research/nursing staff will record oxygen saturation and respiratory rate and assess the subject for sedation and/or intoxication. If respiratory rate drops to <12 breaths per minute or oxygen saturation is <95%, the measurements will be repeated and recorded. If either oxygen saturation or respiratory rate remains outside the pre-specified parameters or the subject appears sedated or intoxicated, the oral maintenance dose of IR morphine 30 mg will be withheld and a study Investigator notified. The withheld dose may be administered later (and the administration time recorded) once it is determined that the subject's status has returned to within a safe range.

On the evening prior to and on the morning of each Qualification/Baseline Hydromorphone Challenge Session day i.e., Day -3, Day -2 and Day -1, subjects will not receive their IR morphine 30 mg dose; therefore, the last active dose of IR morphine 30 mg will be administered a minimum of 12 hours before administration of hydromorphone during the Hydromorphone Challenge Session (see sample IR morphine 30 mg administration schedule in Section 17.1).

On Days -3 to -1, a Qualification/Baseline Hydromorphone Challenge Session will be completed (described in Section 7.1.4). The purpose of the Qualification/Baseline Hydromorphone Challenge Session is to ensure that subjects can discriminate and show positive subjective effects of 6 mg and 18 mg IM hydromorphone compared to IM hydromorphone 0 mg (placebo). After completion of each day of the Hydromorphone Challenge Session, subjects will be assessed by

Version: 2.0, 17NOV2015 Page 33 of 99

research or nursing staff, based upon the same respiratory rate and oxygen saturation criteria described above, to determine if it is safe to resume administration of IR morphine 30 mg maintenance dosing, with dosing time documented. In the event that IR morphine 30 mg dosing is withheld in the afternoon, oral IR morphine 30 mg for the evening dose will be scheduled for no later than the original scheduled administration time in order to maintain consistency between time of last active dose and hydromorphone dose administration the following day. Subjects who are not eligible to continue to the Treatment Phase i.e., do not meet Qualification criteria (Section 8.3) will be discharged from the CRU at approximately 24 hours after administration of the Day -1 IM hydromorphone dose. Prior to discharge, subjects may be offered additional treatment, as needed, per the standard practices of the investigational site. Those subjects who meet Qualification criteria will proceed to the Treatment Phase.

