#### 7.1.3. Treatment Phase

#### 7.1.3.1. Days 0 to 6

On the morning of Day 0 of the Treatment Phase, subjects will receive one of the following treatments (based on randomization in a 1:1 ratio, stratified by gender) to:

- Group A: CAM2038 q1w 24 mg SC injection
- Group B: CAM2038 q1w 32 mg SC injection

Maintenance IR morphine 30 mg will be withheld for at least 12 hours prior to CAM2038 q1w dosing; therefore, the Day -1 evening dose and the Day 0 morning dose of IR morphine 30 mg will be withheld. The Clinical Opiate Withdrawal Scale (COWS; See Section 17.2) will be administered prior to dosing with CAM2038 q1w; in order to be dosed on Day 0, subjects will be required to have a COWS score of  $\geq 8$ , indicative of mild withdrawal.

CAM2038 q1w treatment will be administered at approximately 9:00 am; CAM2038 q1w administration instructions for user (IFU) will be provided in the Manual of Procedures (MOP).

On Days 1 to 3 and Days 4 to 6, subjects will undergo 2 separate Hydromorphone Challenge Sessions (described in Section 7.1.4), with each daily challenge dose of IM hydromorphone administered at approximately 9:00 am (i.e., approximately 24, 48, 72, 96, 120, and 144 hours following Day 0 CAM2038 q1w injection). Safety and pharmacodynamic assessments will be conducted immediately following each dose of hydromorphone administered in each Hydromorphone Challenge Session (maximum 5 hours after Hydromorphone Challenge Session). Plasma samples will also be collected prior to hydromorphone dosing on each day of the Hydromorphone Challenge Sessions.

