#### 9. TREATMENTS

#### 9.1. Treatment Administration

Subjects will be given a short-acting oral opioid, IR morphine 30 mg, QID, for a minimum of 3 days and a maximum of 7 days prior to the Qualification/Baseline Hydromorphone Challenge Session. One additional dose of IR morphine 30 mg may be administered for the first 3 days of stabilization, as needed, at the investigator's discretion. Subjects will not receive IR morphine 30 mg on the evening and morning prior to hydromorphone dosing in the Qualification/Baseline Hydromorphone Challenge Session (Day -3, Day -2, Day -1) and the evening prior to and morning of CAM2038 q1w dosing (Day 0).

Subjects will receive one of the following weekly doses of CAM2038 q1w (BPN FluidCrystal® Injection depot for once weekly administration), 24 mg or 32 mg (BPN base), on two separate days in the study (Day 0 and Day 7). CAM2038 q1w will be administered by SC injection in the subject's buttocks while rotating between right and left buttocks (0.48 mL or 0.64 mL, respectively).

Hydromorphone (10 mg/mL) will be administered in a randomized manner (placebo, 6 mg and 18 mg) once daily during each 3-day Hydromorphone Challenge Session. Hydromorphone will be administered by 1.8 mL IM injection (described below).

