# 17. APPENDICES

# 17.1. Qualification Phase Sample Daily Short-Acting Opioid Administration Schedule

During the Qualification Phase, subjects will be administered IR morphine 30 mg QID for a minimum of 3 days and a maximum of 7 days. For the first 3 days of stabilization, subjects will be permitted to receive one additional dose of IR morphine 30 mg, as needed at the discretion of the Investigator. Therefore, subjects will be permitted to receive a maximum of 150 mg IR morphine per day for the first 3 days, after which the total daily dose will be reduced to 120 mg.

A sample schedule for the 3 Qualification/Baseline Hydromorphone Challenge Session days (Day -3, Day -2, and Day-1) is provided below.

Time	
8:30 am	Start of session (pre-dose Hydromorphone Challenge Session procedures)
9:00 am	Hydromorphone Challenge dose administered, IM
9:00 am – 2:00 pm	Hydromorphone Challenge Session study procedures
2:00 pm	Morphine IR 30 mg dose administered, orally (after all challenge procedures are
	completed)
8:00 pm	Morphine IR 30 mg dose administered, orally

Each morning prior to the start of the Hydromorphone Challenge Session, the COWS (Appendix 17.2) and OOWS (Appendix 17.3) will be administered and the score recorded to assess the degree of opioid withdrawal that the subject may be experiencing.

Version: 2.0, 17NOV2015 Page 83 of 99

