4.3 STUDY DESIGN

This is a multi-site, randomized, double-blind, repeat-dose Phase 2 study to evaluate the degree and duration of action of multiple doses of CAM2038 q1w in blocking the effects of a mu-opioid agonist (hydromorphone) in patients with moderate or severe opioid use disorder. The study will involve 4 phases: Screening, Qualification, Treatment, and Follow-up.

Within approximately 3 weeks of initiating outpatient screening, subjects will be admitted to a clinical research unit (CRU) for the Qualification Phase. Following check in to the CRU, subjects will be transitioned to an oral immediate-release (IR) opioid, morphine 30 mg, 4 times daily (QID) for a minimum of 3 days and a maximum of 7 days prior to the Qualification/Baseline Hydromorphone Challenge Session, which consists of 3 consecutive days of testing. During the Qualification/Baseline Hydromorphone Challenge Session, subjects will not receive their late evening or early subjects will not receive their late evening or early the following morning Morphine -IR; therefore, the last active dose of morphine therefore, the last active dose of morphine -IR will be administered a minimum of 12 hours before administration of the hydromorphone challenge doses.

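### The protocol both withholds and schedules an evening IR morphine dose before the Day -2 and Day -1 challenges and before CAM2038 on Day 0

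*Protocol*

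**What the plan says.** **Text that withholds the evening dose**

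- Protocol 7.1.2.1 applies the rule "On the evening prior to and on the morning of each Qualification/Baseline Hydromorphone Challenge Session day", naming Days -3, -2 and -1. It concludes that "the last active dose of IR morphine 30 mg will be administered a minimum of 12 hours before administration of hydromorphone", and points to Appendix 17.1 for a sample schedule.
- Protocol 9.1 repeats it: "Subjects will not receive IR morphine 30 mg on the evening and morning prior to hydromorphone dosing" in the Qualification session. It adds the evening before and the morning of CAM2038 on Day 0.
- Protocol 7.1.3.1 names the dose: "the Day -1 evening dose and the Day 0 morning dose of IR morphine 30 mg will be withheld". CAM2038 is then given at about 9:00 am.

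**Text that gives an evening dose**

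- Appendix 17.1: "A sample schedule for the 3 Qualification/Baseline Hydromorphone Challenge Session days (Day -3, Day -2, and Day-1) is provided below". Its table has hydromorphone at 9:00 am and two later rows, at 2:00 pm and 8:00 pm, each reading "Morphine IR 30 mg dose administered, orally".
- Protocol 7.1.2.1, in the later paragraph on the challenge sessions: if the afternoon dose is held back, "oral IR morphine 30 mg for the evening dose will be scheduled for no later than the original scheduled administration time". The stated purpose is to keep the gap to the next day's hydromorphone consistent. Section 10.4.5.1 says the same.

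**Text that bears on the interpretation**

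- Table 4, footnote v, and Section 7.2 put the morphine-free interval before CAM2038 at approximately 12 hours.
- SAP 4.3 says that during the Qualification session "subjects will not receive their late evening or early" morning doses, with the same 12-hour minimum.

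**The concern.** One document tells sites to omit the evening dose and also to give it, and the table meant to illustrate the rule does not follow it. The study is multi-site, so two units could each follow the protocol and still bring subjects to the same 9:00 am dose after different periods without morphine.

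This matters in three places.

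- **Eligibility.** Section 8.3 admits subjects on Drug Liking Emax in these sessions: above 55 mm and at least 15 mm over placebo for 6 mg, above 60 mm and at least 20 mm over placebo for 18 mg, and placebo between 40 and 60 mm. Section 7.2 says that stabilization on morphine is meant to protect these scores from distortion by severe withdrawal. COWS and OOWS are recorded before each challenge, but no threshold is attached.
- **Baseline.** There is no placebo depot group. Section 7.2 makes the Qualification session the reference for what happens without CAM2038.
- **Day 0 induction.** Section 7.2 lists time since the last opioid dose among the determinants of precipitated withdrawal. Section 10.6.2 would consider a stricter COWS entry score if more than one such event occurs. If the interval varies by site, those events are harder to interpret.

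**Working it through.** No sample-size or error-rate formula applies. The check has two parts: which evenings are in conflict, and what each reading implies by the clock.

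**1. Evening by evening**

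| Evening of | Next morning's dose | 7.1.2.1 rule, 9.1, 7.1.3.1 | Appendix 17.1 | Direct conflict? |
|---|---|---|---|---|
| Day -4 | Hydromorphone, Day -3 | Withheld | Not covered | No |
| Day -3 | Hydromorphone, Day -2 | Withheld | 8:00 pm, 30 mg | Yes |
| Day -2 | Hydromorphone, Day -1 | Withheld | 8:00 pm, 30 mg | Yes |
| Day -1 | CAM2038, Day 0 | Withheld, by name in 7.1.3.1 | 8:00 pm, 30 mg | Yes, sharpest |

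The later paragraph of 7.1.2.1 and Section 10.4.5.1 time the evening dose relative to hydromorphone on the following day. They bear most directly on the evenings of Days -3 and -2. There they treat the evening dose as the last one before the next challenge, which is the dose that the earlier paragraph of 7.1.2.1 withholds. For Day -1 the conflict rests on Appendix 17.1 against 7.1.3.1 and 9.1.

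**2. Morphine-free interval before 9:00 am**

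Inputs: challenge and CAM2038 dosing at 9:00 am (Appendix 17.1; Section 7.1.3.1); morphine at 2:00 pm and 8:00 pm (Appendix 17.1); minimum interval 12 h (7.1.2.1 and 7.1.3.1). Interval = hours from last dose to midnight + 9.

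- The protocol's own figure: 9:00 am less 12 h is 9:00 pm, the latest last dose allowed.
- 8:00 pm dose given: 4 + 9 = 13 h, which is at least 12 h.
- 8:00 pm dose withheld and 2:00 pm the last dose: 10 + 9 = 19 h, which is at least 12 h.
- Difference: 19 - 13 = 6 h.

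The 13 h figure comes from times printed in one table. The 19 h figure is inferred: it applies the withholding rule to that table and takes the remaining row as the last dose. The documents state no 19-hour interval.

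**3. Morphine on a challenge day**

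- Both rows given: 2 x 30 mg = 60 mg.
- 8:00 pm row withheld: 1 x 30 mg = 30 mg.

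**4. Can other text decide between the readings?**

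The 12-hour minimum cannot, because both pass. The approximately 12 hours in Table 4 footnote v and Section 7.2 lies closer to 13 h than to 19 h. The SAP's late-evening wording also fits 13 h: with four doses a day, 2:00 pm and 8:00 pm would be given, and a late-evening and an early-morning dose would be withheld. The protocol never sets this out.

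**The case against.** The strongest reply is that there is a single regimen loosely described. Morphine is given four times daily. On challenge days Appendix 17.1 shows two doses, and the SAP says that the two omitted are the late-evening and early-morning ones. Section 7.1.2.1 cites the appendix as an illustration of its own rule, and the repeated approximation of 12 hours agrees with an 8:00 pm last dose. On this view the only fault is the word evening, and 19 hours is a reader's construction.

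Much of this stands. The late-evening reading is a plausible intent, and 19 hours is not a documented schedule. But the protocol uses evening dose both for the dose given (7.1.2.1, later paragraph) and for the dose withheld (7.1.3.1). Its only clock times for morphine are in the appendix, and nothing in it says that 8:00 pm is not the evening dose. Calling the table a sample does not help, since a sample should comply with the rule it illustrates. Sites should not need the SAP to resolve a dosing instruction.

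A reader might also infer more than the documents support.

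- **That every challenge is affected.** Twelve of the 15 challenge days fall in the Treatment Phase, where no maintenance morphine is scheduled. The appendix does not cover the evening of Day -4 either, so it shows no conflict for the Day -3 challenge.
- **That the 12-hour minimum is broken.** Neither reading breaks it.
- **That Day 0 dosing is uncontrolled.** COWS of at least 8 is required under either reading, and Section 10.6.2 specifies assessments if precipitated withdrawal occurs. The requirement is a floor without an upper limit, so it narrows differences in withdrawal state but does not remove them.
- **That the primary result is biased.** The primary analysis compares 6 mg and 18 mg with 0 mg within subjects, in the four sessions under CAM2038. Qualification-phase morphine timing does not enter that contrast directly.

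**Conclusion.** The conflict is real, is in current protocol text, and concerns three evenings: those before Day -2, Day -1 and Day 0. It is plainest for Day -1, where 7.1.3.1 withholds the evening dose by name and Appendix 17.1 lists one at 8:00 pm. Confidence in that mismatch is high.

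The two readings differ by 6 hours without morphine (13 against 19) and by one 30 mg dose on each challenge day. This assumes that 2:00 pm is the last dose when 8:00 pm is withheld. The wording elsewhere favours the 13-hour reading as a matter of interpretation, but it is not explicit enough to ensure that sites act alike.

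The consequence is reduced comparability of Qualification and baseline Drug Liking scores, and of withdrawal state at Day 0 induction. That sites would in fact diverge is possible but not shown. The documents give no withdrawal scores by hours since last dose, so the size of any effect is unknown. The claim goes no further than qualification, baseline and induction. It is worth correcting because it touches eligibility and safety and is cheap to correct.

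**What to change.** Reconcile Protocol 7.1.2.1 (both the withholding rule and the later evening-dose text), 7.1.3.1, 9.1, 10.4.5.1, Table 4 footnote v, Appendix 17.1 and SAP 4.3 into one schedule. It should state, for each evening from Day -4 to Day -1, which IR morphine doses are given and which are withheld, identified by clock time rather than by the word evening. The evening of Day -4 should be included because the appendix is silent on it. All sites should follow the same schedule. Which schedule is right is for the sponsor's clinical staff; nothing here favours one on clinical grounds.

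The cost is a clarification amendment and a matching edit to the SAP's design summary. No procedures, visits or subjects are added.
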